Clinical Study Protocol Synopsis

Title	A Multicenter, Randomized, Open-label, Crossover, Phase 2 Study to Evaluate the Safety and Pharmacokinetics of IgPro20 (subcutaneous immunoglobulin, Hizentra [®]) and IgPro10 (intravenous immunoglobulin, Priviligen [®]) in Adults with Systemic Sclerosis (SSc)
Study Number	IgPro20_2001
Sponsor	CSL Behring (CSLB)
Phase	Phase 2
Study Product	IgPro20 (Hizentra) IgPro10 (Priviligen)
Indication	Systemic Sclerosis (SSc)
Study Summary and Overview	This is a prospective, multicenter, randomized, open-label, crossover study to investigate the safety, tolerability, relative bioavailability and pharmacokinetics (PK) of weekly subcutaneous (SC) administration of IgPro20 and intravenous (IV) administration of Ig Pro10 every 4 weeks (over 2 to 5 consecutive days) in subjects with diffuse cutaneous SSc (dcSSc) over 16 week treatment periods.
Primary Objectives	The primary objective of the study is to evaluate the safety of IgPro20 in adults with dcSSc.
Primary Endpoints	
The primary endpoint is the safety of IgPro20 based on adverse events (AEs) and the change in other clinical tests measured by treatment, treatment sequence, combination of treatment, at the end of each treatment period (Period 1, Week 16; Period 2, Week 32; combination of treatment, Week 32):
 
 • Number and percentage of subjects with AEs, treatment-emergent AEs, serious AEs, and AEs of special interest (total, severity, causality, and outcome) • Number and percentage of subjects with AEs categorized as infusion site reactions (ISRs) (total, severity, causality and outcome) • Rate of ISRs per subject and per infusion • Onset and duration of ISRs • Changes from baseline in vital signs and body weight, clinical laboratory tests, electrocardiogram (ECG), and pulmonary function tests (PFTs)

Secondary Objectives	
The secondary objectives of the study are to evaluate:
 
 • Relative bioavailability of IgPro20 • PK of IgPro20 • PK of IgPro10 • Safety of IgPro10

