2.1.2 Primary Endpoints

The primary endpoint of the study is the safety of IgPro20 based on:

Safety Endpoints	Summary Measure
AEs, including any AEs, treatment-emergent adverse events (TEAEs), serious adverse events (SAEs), and adverse events of special interest (AESIs)	
AEs measured by treatment, treatment sequence, combination of treatment, and treatment period (Period 1, Week 16; Period 2, Week 32; combination of treatment, Week 32):
 
 Number and percentage of subjects with AEs, TEAEs, SAEs, and AESIs (total, severity, causality, and outcome) Number and percentage of subjects with AEs categorized as ISRs (total, severity, causality and outcome) Rate of ISRs per subject and per infusion Onset and duration of ISRs
Change in other clinical tests	
Changes from baseline as measured by treatment, treatment sequence, combination of treatment and treatment period:
 
 Vital signs Body weight Clinical laboratory tests Electrocardiogram (ECG) Pulmonary function tests (PFTs)

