10.3.2 Analyses of Primary Endpoints

10.3.2.1 Safety of IgPro20

Safety data collected while subjects are treated with IgPro20 will be summarized by treatment sequence. All AEs will be coded by the Medical Dictionary for Regulatory Activities in System Organ Class and Preferred Term. Treatment-emergent adverse events, defined as AEs reported at or after the start of the first infusion in the study, will be summarized in number and percentages by treatment sequence. Summaries of TEAEs by

severity, causal relationship, seriousness, and leading to interruption and / or withdrawal will be provided.

Infusion site reactions will also be summarized separately following the analyses for all TEAEs. Additional summary statistics including 95% CIs will be presented for rate of ISRs per subject and per infusion. Descriptive statistics of time to onset and duration of ISRs will be presented. Detailed information about ISRs related to infusion sites will be provided.

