4.2 Objectives and Endpoints

Objectives	Endpoints
Primary	
To evaluate the safety of IgPro20 in adults with dcSSc	
 Number and percentage of subjects treatment-emergent AEs (TEAEs), serious AEs (SAEs), and AEs of special interest (AESIs) (total, by severity, by causal relationship) Number and percentage of subjects with AEs categorized as infusion site reactions (ISRs) (total, by severity, by causal relationship) Rate of ISRs per subject and per Infusion Onset and duration of ISRs Changes from baseline in vital signs and body weight, clinical laboratory tests, electrocardiogram (ECG), and pulmonary function tests (PFTs)

Objectives	Endpoints
Secondary	

To evaluate:
 
 • Relative bioavailability of IgPro20 • PK of IgPro20 • PK of IgPro10 • Safety of IgPro10 	
 • IgPro20 relative bioavailability (%F) • IgPro20 PK parameters (area under the curve [AUC]_{0-tau}, AUC_{0-last}, maximum [peak] plasma drug concentration [C_{max}], trough plasma drug concentration [C_{trough}]) • IgPro10 PK parameters (AUC_{0-tau}, AUC_{0-last}, C_{max}, C_{trough}) • The safety of IgPro10 based on: 
 ○ Number and percentage of subjects with TEAEs, SAEs, AESIs, and ISR (total, by severity, by causal relationship) ○ Changes from baseline in vital signs and body weight, clinical laboratory tests, ECG, and PFTs

CCI
 
 • CCI • • • • • • 	
 • CCI • • • • • •

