4.7 Interim Sample Size Re-estimation

Sample size re-estimation is not planned for this study.

5 Changes in the Conduct of Planned Analyses

The primary endpoint (CSP 2.1.2) requests to summarize AEs, TEAEs, AESIs, and SAEs in total and by severity and causality. In deviation to this, the summary of AEs will be restricted to TEAEs only.

In section CSP 2.2.2 “Secondary Endpoints” C_{trough} is defined as “minimum plasma drug concentration”. This is corrected to “trough plasma drug concentration”.

In section CSP 10.3.2.1 “Safety of IgPro20” 95% confidence intervals (CI) are requested for the rate of ISR per subject and per infusion. The CIs for the rate of ISR per infusion will not be calculated as the infusions are not statistically independent.

The Full Analysis Set (section CSP 10.2.1) is renamed to ITT Analysis Set, and the description was reworded for clarity. The definition of the set is not changed.

Section 10.4.2 of the CSP (Interim Analysis) states:

"An interim analysis is planned after all subjects randomized to Sequence A have finished IgPro20 treatment (Treatment Period 1). This interim analysis is planned for safety review and reporting."

The timing and purpose of the Interim Analysis has changed (see Section 4.6 of this SAP).

CSP section 10.3.3.1 requires "... subject as a random effect ..." in the model to assess relative bioavailability. This effect will not be applied.

6 Study Analysis Sets

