Adverse events associated with COVID-19, which can include a clinically significant laboratory finding like a positive test result for COVID-19, will be reported by investigators. COVID-19 associated adverse events are identified via MedDRA coding. Relevant adverse events will be identified for reporting by the broad COVID-19 standard MedDRA query (SMQ). All COVID-19 associated adverse events will be included in standard AE tables.

An overview summary table of COVID-19 associated treatment-emergent adverse events (TEAEs), including number and percentages of subjects as well as the number of events, will be provided for the following:

- Any TEAE (related/not related)
- Any serious TEAE (related/not related)
- TEAE resulting in death (related/not related)
- TEAE leading to permanent discontinuation of IP (related/not related)
- TEAE leading to interruption of IP (related/not related)
- TEAE leading to withdrawal from study (related/not related)
- TEAE by severity (mild, moderate, severe, missing)

A listing showing all COVID-19 associated adverse events will be provided.

A descriptive table will be generated for all COVID-19 associated TEAEs by PT, including number of subjects, percentages of subjects, and the number of events.

COVID-19 Vaccinations

Sites will be prompted to inquire whether a subject has received a COVID-19 vaccination and to record each dose of the vaccine on the concomitant medications form along with the exact date of administration and manufacturer of the vaccine. Standardised Drug Grouping (SDG) from WHO Drug Dictionary will be utilized to identify COVID-19 vaccines using the narrow SDG 'Vaccines for COVID-19'.

For subjects receiving COVID-19 vaccination during the study all treatment-emergent adverse events occurring within 7 days of COVID-10 vaccination will be summarized by System Organ Class and preferred term.

Visit Modality, Missed Visits and Missing Assessments

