11.2 Adverse Events

All AEs will be coded by the Medical Dictionary for Regulatory Activities. System organ class (SOC), high-level group term (HLGT), high-level term (HLT), preferred term (PT), and lower-level term (LLT) will be provided in the AE dataset.

Summaries will be presented for the following combinations of Treatment Sequence and Treatment Period (respective Treatment Sequences [A/B] and Treatment Periods [1/2] are given in parentheses):

- IgPro20 (A/1 and B/2)
- IgPro10 (A/2 and B/1)
- IgPro20/ Treatment Period 1 (A/1)
- IgPro20/ Treatment Period 2 (B/2)
- IgPro10/ Treatment Period 1 (B/1)
- IgPro10/ Treatment Period 2 (A/2)
- Total (A/1, A/2, B/1, and B/2)

Infusion site reactions (ISR) comprise all AEs reported within the MedDRA HLTs “Administration site reactions NEC” or “Infusion site reactions”.

Summaries of AEs created to assess the COVID-19 impact are described in Section 7.4.

Refer to Section 11.3 for the definition of Adverse Events of Special Interest (AESIs).

- An overview summary of TEAEs, including number of subjects, percentages of subjects, and the number of events by Treatment Sequence, treatment, and Treatment Period including the following:
 - Any TEAE
 - Any serious TEAE
 - TEAEs leading to interruption of IP
 - TEAEs leading to permanent discontinuation of IP
 - TEAEs leading to withdrawal from study
 - Temporally associated TEAEs
 - Treatment-emergent AESIs (Hemolysis, TEE, Acute Renal Injury)
 - Any serious treatment-emergent AESIs
 - Treatment-emergent AESIs leading to permanent discontinuation of IP
 - Treatment-emergent AESIs leading to withdrawal from study

- Related treatment-emergent AESIs
 - Treatment-emergent AESIs by Grade
 - Treatment-emergent AESIs Grade 3 and above
 - TEAEs by causality (related to IP)
 - TEAEs by severity (mild, moderate, severe)
 - TEAEs by outcome (“recovered or resolved” vs. all other outcomes combined)
 - Any ISR
 - ISRs leading to interruption of IP
 - ISRs leading to permanent discontinuation of IP
 - ISRs leading to withdrawal from study
 - ISRs by causality (related to IP)
 - ISRs by severity (mild, moderate, severe)
 - ISRs by outcome (“recovered or resolved” vs. all other outcomes combined)
- The following descriptive tables will be generated for TEAEs, including number of subjects, percentages of subjects, and the number of events:
 - TEAEs by SOC and PT
 - TEAEs by PT
 - TEAEs by SOC, PT, and maximum severity (without number of events)

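### The protocol's primary safety endpoint is reported by outcome; the SAP endpoint drops outcome without declaring it, and the tables keep only a two-level split for TEAEs and ISRs

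*Protocol*

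**What the plan says.** **Protocol.** Section 2.1.2 sets the first summary measure of the primary endpoint as "Number and percentage of subjects with AEs, TEAEs, SAEs, and AESIs (total, severity, causality, and outcome", and the synopsis agrees: "Number and percentage of subjects with AEs, treatment-emergent AEs, serious AEs, and AEs of special interest (total, severity, causality, and outcome". Both make outcome a breakdown for ISRs as well. Section 2.2.2 repeats outcome for the safety of IgPro10, a secondary endpoint. The analysis text in Section 10.3.2.1 is less complete. It promises TEAE summaries by "severity, causal relationship, seriousness, and leading to interruption and / or withdrawal will be provided" and does not mention outcome.

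**SAP.** Section 4.2 gives the primary endpoint as "Number and percentage of subjects treatment-emergent AEs (TEAEs), serious AEs (SAEs), and AEs of special interest (AESIs) (total, by severity, by causal relationship". The ISR line and the IgPro10 line stop at the same three breakdowns. Section 5 restates the protocol's request as total, severity and causality. Its one declared change to this endpoint is that "the summary of AEs will be restricted to TEAEs only". Section 11.2 has an outcome row for all TEAEs and another for ISRs, each setting recovered or resolved events against the rest ("vs. all other outcomes combined"). Section 7.4, for COVID-19-associated events only, includes a row "TEAE resulting in death (related/not related".

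**The concern.** Outcome is part of the primary endpoint in the protocol but not in the SAP. Section 5 exists to tell the reader about such changes. Because it paraphrases the protocol without outcome, someone relying on it would not learn that anything had been removed.

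What remains in the tables is not equivalent. A single pooled category can hold a fatal event, one that left lasting damage and one still settling. Lasting local harm matters here: Protocol 1.1 justifies the study partly because skin fibrosis and ulceration in systemic sclerosis may change the safety of subcutaneous infusion, and Section 1.4.1.1 lists ulceration-like ISRs among the important identified risks of IgPro20. The endpoint is a number and percentage of subjects, so the tables by treatment are where a reader will look for it.

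**Working it through.** The plan gives no figure to reproduce, so the check sets the texts side by side.

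**Step 1. What is required and what is planned.**

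| Event group | Outcome in Protocol 2.1.2 | Outcome in SAP 4.2 | Outcome row in SAP 11.2 |
|---|---|---|---|
| All AEs | yes | no | none; restriction to TEAEs declared in SAP 5 |
| TEAEs | yes | no | yes, two levels |
| SAEs | yes | no | none |
| AESIs | yes | no | none named; SAP 11.3 ambiguous |
| ISRs | yes | no | yes, two levels |

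The declared restriction removes one group: 5 − 1 = 4. Of those four, 2 have an explicit outcome row. In 0 of 4 does an explicit row separate fatal or lasting outcomes from the other unresolved ones.

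**Step 2. Is the narrowing declared?** No. The restriction to TEAEs explains the first row of the table and nothing else. Section 5 leaves outcome out when it describes what the protocol asks for.

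**Step 3. Do other planned summaries supply the missing information?** Only in part.

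- Severity has three levels, mild to severe (Protocol 9.2), so it cannot mark a death.
- AESIs are tabulated by grade. Protocol 8.1.1.2 defines Grade 5 as death for hemolysis, but the protocol text gives no such scale for thromboembolic events.
- A fatal AE meets the seriousness definition (Protocol 9.1.2). It is therefore counted in the serious TEAE row and in serious TEAEs by SOC and PT, but nothing there says that it was fatal.
- The fatal row in SAP 7.4 covers COVID-19-associated events only.
- ISR duration is summarised, but SAP 8.1.2 sets duration to missing when the end date is missing. An ISR that never resolves therefore drops out of that summary.

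**Step 4. Are the data there?** Yes. Protocol Table 1 names outcome among the attributes evaluated for every AE, and the two-level rows in SAP 11.2 already presuppose a recorded outcome.

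**Step 5. Where else does it carry through?** SAP 4.6 takes the interim safety tables as a subset of the final ones, without modification, so the interim review has at most the same outcome rows.

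**The case against.** The strongest reply is that outcome is still analysed. SAP 11.2 gives it with subjects, percentages and events, by sequence, treatment and period. The protocol defines no outcome categories and its own analysis section omits outcome, so a two-level row breaks no stated rule. SAP 11.3 says AESI tables will be made in a similar way to the TEAE tables, and the shells are in separate documents. SAEs are followed to resolution, stabilisation, loss to follow-up or death (Protocol 9.5), so few still-settling serious events should remain at the final analysis. With about 26 subjects, a listing shows each death in full.

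Much of this stands. The protocol is not fully consistent with itself, the AESI position is unclear rather than plainly missing, and the number of outcome levels is partly a matter of judgement. It does not answer three things: serious TEAEs have no outcome row, the endpoint definition changed without declaration, and a listing does not deliver a number and percentage of subjects.

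A reader might go further and infer that a death unrelated to COVID-19 would appear only in a listing, or that the report could not show fatal or lasting harm. The documents do not support that. Such a death is also counted among serious TEAEs by product. SAP 11.2 provides listings of deaths, serious TEAEs, AESIs, ISRs and all AEs, and SAP 7 puts sequence and period on every listing, so each event can be attributed to a treatment.

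**Conclusion.** The point holds as an undeclared narrowing of the primary safety endpoint. Followed as written, the SAP would not tabulate outcome for SAEs, would leave AESIs uncertain, would pool fatal and lasting outcomes with other unresolved ones for TEAEs and ISRs, and would label fatal events in a summary only if they were COVID-19-associated. The loss lies in the summary tables by treatment and not in the whole report. No estimate, denominator or analysis set changes. It should be corrected, but it does not threaten the study's conclusions.

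One could try to size it by projecting deaths from the 74.9% five-year survival cited in Protocol 1.1. That figure describes systemic sclerosis generally, from diagnosis. This trial excludes significant pulmonary arterial hypertension, recent renal crisis, cardiac insufficiency and previous thrombosis. The chance of a death would in any case not measure what is lost by listing it without a summary row, so no probability is offered.

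The verdict assumes that the eCRF records more than two outcome categories, which the pooled wording implies but the documents do not list, and that the unseen shells follow the text of SAP 11.2.

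**What to change.** 1. In SAP 4.2, restore outcome to the AE and ISR lines of the primary endpoint and to the matching IgPro10 line.
2. In SAP 5, correct the paraphrase of Protocol 2.1.2 so that it includes outcome. Declare and justify there any narrowing that is still intended.
3. In SAP 11.2, replace the two-level split with one row per outcome category recorded in the eCRF, for TEAEs, serious TEAEs, AESIs and ISRs, by treatment. This also settles the ambiguity in SAP 11.3.
4. Add to the main overview a row for TEAEs resulting in death, split by relatedness, as SAP 7.4 already does for COVID-19 events.

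The cost is SAP wording and a few table rows, using data already collected. The downside is slightly longer tables with small cells.
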